definitive RT+ADT. Simon's optimal two-stage design (Simon, 1989) will be used for conducting the trial. The null hypothesis is that the proportion of patients with PSA <0.5 without any treatment is 5%, and the alternative hypothesis is that the proportion of patient with PSA <0.5 at 6 weeks into treatment is 30% or higher. The trial is carried out in two stages. In stage I, a total number of 5 patients is accrued. If there are 0 response (PSA < 0.5) among these 5 patients, the study will be early stopped. Otherwise, additional 18 patients will be accrued in stage II, resulting in a total number sample size of 23. If there are 4 or more responses (PSA < 0.5) among these 23 patients, we reject the null hypothesis and claim that the treatment is promising. The design controls the type I error rate at one-sided 0.025 and yields the power of 80%. If we reject the null hypothesis, seven additional patients will be enrolled to explore the association between biomarkers and clinical activities. Patients receive ADT x 2 years and will start 3 months before RT. Abemaciclib will start with initiation of ADT and pause 2 weeks prior to start of RT. Abemaciclib will resume with the first ADT administration post-radiation, which typically is at 1 month post radiation therapy. Abemaciclib and ADT will continue for a total ADT period of 24 months. Patients will have laboratory evaluation every 2 weeks for the first 2 months and monthly thereafter for the next 2 months. Patients are also seen and evaluated every 4 weeks with laboratory evaluation. Labs may be drawn at outside laboratories at the PI's discretion. For toxicity or adverse event, patients will undergo labs, physical examination and grades of toxicities will be determined using NCI CTCAE version 4.03. Disease response and biochemical failure will be assessed by PSA prior to the start of radiation and every 3 months following the end of radiotherapy and by the investigator (physical exam). The determination of disease progression for the study requires a confirmation of 3 consecutive rises of PSA 3 months apart in the setting of testosterone recovery. Patients will be withdrawn from study for following toxicities,

Toxicity Category	Drug-Related Toxicity/Grade
Hematologic	Grade 4 neutropenia for ≥ 5 days
	Febrile neutropenia: ANC < 1000/mm ³ with a single temperature of $>38.3^{\circ}\text{C}$ (101°F) or a sustained temperature of $\geq 38^{\circ}\text{C}$ (100.4°F) for more than one hour.

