All patients will receive Abemaciclib at 150 mg BID PO dose. The trial is carried out in two stages. In stage I, a total number of 5 patients are accrued. If there are 0 response (PSA< 0.5) among these 5 patients, the study will be early stopped. Otherwise, additional 18 patients will be accrued in stage II, resulting in a total number sample size of 23. If there are 4 or more responses (PSA< 0.5) among these 23 patients, we reject the null hypothesis and claim that the treatment is promising. The design controls the type I error rate at one-sided 0.025 and yields the power of 80%. If we reject the null hypothesis, seven additional patients will be enrolled to explore the association between biomarkers and clinical activities. To account for 10% screen failure, total of 33 patients will be recruited to the study.

Table 1: Toxities leading to withdrawal of subjects

Toxicity Category	Drug-Related Toxicity/Grade
Hematologic	Grade 4 neutropenia for ≥ 5 days
	Febrile neutropenia: ANC $< 1000/\text{mm}^3$ with a single temperature of $>38.3^\circ\text{C}$ (101°F) or a sustained temperature of $>38^\circ\text{C}$ (100.4°F) for more than one hour.
	Neutropenic infection: Grade ≥ 3 neutropenia with Grade ≥ 3 infection
	Grade ≥ 4 Anemia
	Grade ≥ 4 thrombocytopenia or Grade ≥ 3 thrombocytopenia with Grade ≥ 3 hemorrhage
Non-hematologic	Grade 2 ($>3.0 \times \text{ULN}$) ALT/AST with total bilirubin $>2 \times \text{ULN}$, in the absence of cholestasis Grade 3 or 4 non-hematologic toxicity with the following exceptions: 
Asymptomatic electrolyte abnormality that resolve within 48 hours.Grade 3 headache lasting <48 hours

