Hematologic toxicities including neutropenia, leukopenia, anemia, and thrombocytopenia have been observed in patients treated with abemaciclib, and causality has been established. Severe (Grade 3 and 4) neutropenia was observed in patients receiving abemaciclib. Patients should be monitored closely for signs of infection, anemia, and bleeding. **Table 9 provides guidance on dose modification and management of hematologic toxicities.**

Table 9: Dose Modification and Management — Hematologic Toxicities

Monitor complete blood counts prior to the start of abemaciclib therapy, every 2 weeks for the first 2 months, monthly for the next 2 months, and as clinically indicated.	
CTCAE Grade	Abemaciclib Dose Modifications
Grade 1 or 2	No dose modification is required.
Grade 3	Suspend dose until toxicity resolves to \leq Grade 2. Dose reduction is not required.
Grade 3, recurrent, or Grade 4	Suspend dose until toxicity resolves to \leq Grade 2. Resume at next lower dose.
Patient requires administration of a blood cell growth factor	Suspend abemaciclib dose for at least 48 hours after the last dose of blood cell growth factor and until toxicity resolves to \leq Grade 2. Resume abemaciclib at next lower dose unless the dose was already reduced for the toxicity that led to the use of the growth factor.

General Guidance for Non-hematologic Toxicities (excluding diarrhea, ILD/Pneumonitis and increased ALT/AST) Monitoring

Table 10: Dose Modification and Management — Non-hematologic Toxicities Excluding Diarrhea and ALT Increased

CTCAE Grade	Abemaciclib Dose Modifications
Grade 1 or 2	No dose modification is required.
Persistent or recurrent Grade 2 toxicity that does not resolve with maximal supportive measures within 7 days to baseline or Grade 1	Suspend dose until toxicity resolves to baseline or Grade 1. Resume at next lower dose.
Grade 3 or 4	

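### Table 1 withdraws patients for drug-related Grade 4 anemia, Grade 4 thrombocytopenia and prolonged Grade 4 neutropenia; Table 9 restarts them at a lower dose, and no text says which governs

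*Combined protocol and SAP*

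**What the plan says.** **The withdrawal list.** The synopsis (Overall design) introduces it as mandatory: "Patients will be withdrawn from study for following toxicities". Section 4.1.1 repeats it as "Table 1: Toxities leading to withdrawal of subjects". Both copies are limited to drug-related toxicities. The hematologic entries that matter here are "Grade 4 neutropenia for ≥ 5 days", "Grade ≥ 4 Anemia", "Grade ≥ 4 thrombocytopenia or Grade ≥ 3 thrombocytopenia with Grade ≥ 3 hemorrhage" and "Neutropenic infection: Grade ≥ 3 neutropenia with Grade ≥ 3 infection". The non-hematologic part includes "Grade 3 or 4 non-hematologic toxicity with the following exceptions". The exceptions are an asymptomatic electrolyte change that clears within 48 hours and a Grade 3 headache shorter than 48 hours.

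**The dose-modification tables in 6.4.3.** The text introducing Table 9 names neutropenia, leukopenia, anemia and thrombocytopenia. For a first Grade 3 event the table says to hold abemaciclib until Grade 2 or better, with no dose reduction needed. For "Grade 3, recurrent, or Grade 4" it says to hold until Grade 2 or better and restart one dose level down. Table 4 gives that level as 100 mg BID. Table 7 says to hold and restart one level down for Grade 3 ALT/AST that has not resolved within 7 days. It stops the drug only for Grade 4 ALT/AST, or for Grade 2 or higher with bilirubin above 2 x ULN without cholestasis.

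**The general rules.** Section 6.4.2 has both study drugs withheld for drug-related Grade 4 hematologic toxicity and for non-hematologic toxicity of Grade 3 or higher, laboratory abnormalities included. It requires that the medical monitor be notified before a restart. Section 6.5 lists reasons for permanent discontinuation, among them an undefined unacceptable toxicity and a toxicity not recovered in 2 weeks. Neither 5.3 nor 6.5 refers to Table 1.

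**The concern.** For the same drug-related event, one part of the protocol ends abemaciclib and another gives instructions for restarting it. Two things depend on which part a treating team follows.

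The first is the patient's exposure. After a Grade 4 cytopenia he is either stopped for good or re-exposed at 100 mg BID. Section 5.4 has patients entered at three UAB locations, so different handling is possible even in a single-center trial.

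The second is a reported result. Tolerability and feasibility is a secondary objective, and 10.2.2 reports the number and percentage of patients with adverse events that led to study drug discontinuation. That count would partly reflect which table was consulted as well as how the drug was tolerated.

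**Working it through.** The plan states no figure for this point, so the check is mainly a comparison of text.

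**Step 1: set the rules side by side (drug-related events).**

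| Event | Table 1 / synopsis | Tables 9 and 7 | Result |
|---|---|---|---|
| Anemia, Grade 4 | Withdraw | Table 9: hold, restart one level down | Conflict |
| Thrombocytopenia, Grade 4 | Withdraw | Table 9: hold, restart one level down | Conflict |
| Neutropenia, Grade 4, 5 days or more | Withdraw | Table 9: hold, restart one level down (no duration limit) | Conflict |
| Neutropenia, Grade 4, under 5 days, no fever or Grade 3 infection | Not listed | Table 9: hold, restart one level down | No conflict |
| Neutropenia, Grade 3, with infection of Grade 3 or higher | Withdraw | Table 9, Grade 3 row: hold, no reduction needed; no exception made | Conflict |
| Thrombocytopenia, Grade 3, with hemorrhage of Grade 3 or higher | Withdraw | Table 9, Grade 3 row: hold, no reduction needed; no exception made | Conflict |
| ALT/AST, Grade 3, unresolved at 7 days | Withdraw, by inference from the general non-hematologic line | Table 7: hold, restart one level down | Conflict, by inference |

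**Step 2: look for a rule of precedence.** Sections 2.7, 5.3, 6.1.5, 6.4.2 and 6.5 contain none. Section 2.7 says that dose reduction is possible, anemia included, but does not mention Table 1. Section 6.4.2 is a third instruction for the same events: withhold, then restart after notification. Section 6.4.3.2 has abemaciclib restarted at a reduced level after growth factors and makes no exception for Table 1 events.

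**Step 3: scale.** The documents give no rate for the Table 1 events. Section 2.3.2 reports Grade 3 or higher neutropenia in up to 20% of patients in breast cancer studies, but that is a much wider category than Grade 4 for 5 days or more. No rate is assumed here. What follows is arithmetic that would apply to any one patient in a trial of this size.

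- One patient is 1/23 = 4.3 percentage points, or 1/30 = 3.3 points with the seven additional patients.
- Exact (Clopper-Pearson) 95% intervals: 0/23 gives 0 to 14.8%, 1/23 gives 0.1 to 21.9%; 0/30 gives 0 to 11.6%, 1/30 gives 0.1 to 17.2%.
- The chance of at least one affected patient is 1 - (1 - p)^n, where p is the combined rate of these events. It passes 50% when p exceeds 1 - 0.5^(1/23) = 3.0%, or 1 - 0.5^(1/30) = 2.3%. These are hypothetical thresholds; the documents do not say where p lies.

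The shift per patient is an upper limit, because some of these patients would stop anyway under 5.3 or 6.5.

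**The case against.** **Table 1 prevails as the mandatory rule.** The synopsis says that patients will be withdrawn, while Table 9 is introduced as guidance. A specific mandatory list would ordinarily override a general guide. Table 9's Grade 4 row would still have a use, for Grade 4 leukopenia and for Grade 4 neutropenia under 5 days. This makes Table 1 the natural default, and it means that the trial is not unworkable, as a reader might infer. But it remains an inference. Where 6.4.3 intends a permanent stop it says so: Table 6 for Grade 3 or 4 ILD/pneumonitis, and two rows of Table 7. Table 9 has no such row. On this reading its Grade 4 row would never apply to drug-related anemia or thrombocytopenia, although the text above it names both.

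**Safeguards limit re-exposure.** The medical monitor must be notified before a restart (6.4.2). Toxicity not recovered in 2 weeks ends treatment unless the monitor approves continuing (6.5). A delay of more than 7 days in cycle 1 ends treatment (5.3). These reduce the risk. They do not settle the rule for a patient who recovers within those limits, and notification is not approval.

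**Table 1 does not name Grade 3 ALT/AST.** This is correct. Its only explicit liver entry, Grade 2 ALT/AST with raised bilirubin, agrees with Table 7's discontinuation row. Grade 3 is reached through the general non-hematologic line, which does not except it. Section 6.4.2 supports that reading by counting laboratory abnormalities as non-hematologic toxicity. The conflict with Table 7 is therefore plausible but inferred, and weaker than the hematologic ones.

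**Wider readings.** A reader might infer that withdrawn patients are lost to the PSA endpoint. The documents do not support this: the Schedule of Assessments marks PSA in the end-of-treatment and follow-up column, 4.1.3 asks for continued response monitoring, and 5.3 asks that outcome be documented. A reader might also extend the conflict to Grade 3 or 4 events in Tables 5 and 10. Their action cells are empty in the text available, possibly because merged cells were lost, so nothing is concluded from them.

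**Conclusion.** The point holds for drug-related Grade 4 anemia, Grade 4 thrombocytopenia and Grade 4 neutropenia of 5 days or more. It holds likewise for the two Grade 3 combinations that Table 9 does not except. For Grade 3 ALT/AST unresolved at 7 days it holds by inference. The written safety rules contradict each other and no text resolves them.

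The consequences are inconsistent handling of re-exposure after severe drug-related toxicity and an inconsistent discontinuation count in 10.2.2. The frequency is unknown, and the notification and 2-week rules mitigate the risk in part. The shift of up to 4.3 or 3.3 points per patient shows scale only and is not a forecast. No effect on the primary endpoint, power, type I error or the stage I rule is claimed. Whether withdrawal means leaving the study or leaving treatment is a separate question and is not part of this point. The change should be made because it concerns patient safety and is cheap.

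**What to change.** 1. **Table 9.** Add a row: *Drug-related hematologic event listed in Table 1: discontinue abemaciclib.* Limit the Grade 3 and Grade 4 hold-and-restart rows to events not listed in Table 1. The drug-related qualifier must stay, because without it an unrelated Grade 4 anemia would force a permanent stop that Table 1 does not require. Dose reduction for recurrent Grade 3 anemia remains available, in line with 2.7.
2. **Grade 3 ALT/AST.** Choose one rule. Either add *Grade 3 ALT/AST managed per Table 7* to the exceptions in both copies of the withdrawal list, or change drug-related Grade 3 ALT/AST in Table 7 to *Discontinue abemaciclib*. Persistent or recurrent Grade 2 can stay as it is.
3. **Sections 6.4.2 and 6.5.** State that drug-related events listed in Table 1 lead to permanent discontinuation of abemaciclib and are not eligible for restart. This also covers the restart after growth factors in 6.4.3.2.

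The cost is wording only, with no added patients, procedures or data fields. The downside is that a few patients who would have restarted at 100 mg BID stop abemaciclib. If the ALT/AST exception is chosen, re-exposure after Grade 3 ALT/AST remains possible, but under one stated rule.

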6.4.3.1. Therapy for Febrile Neutropenia

Patients experiencing febrile neutropenia, especially with diarrhea or dyspnea, should be managed in a hospital setting according to standard procedures, with the urgent initiation of IV antibiotic therapy. Events that require a patient to be hospitalized are considered SAEs

6.4.3.2. Growth Factor Therapy

Growth factors should not be administered to a patient to satisfy study inclusion criteria. Growth factors may be administered in accordance with ASCO guidelines (Smith et al. 2015). Dosing of abemaciclib must be suspended if the administration of growth factors is required and must not be recommenced within 48 hours of the last dose of growth factors having been administered. Following the administration of growth factors, the dose of abemaciclib must be reduced to the previous dosing level on recommencement, if a dose reduction for the specific event necessitating the use of the growth factors has not already occurred.

6.5. Criteria for permanent discontinuation of study drug(s)

Subjects may withdraw consent at any time for any reason or be withdrawn from the study at the discretion of the investigator should any untoward effect occur. In addition, a subject may be withdrawn by the investigator or the sponsor if enrollment into the study is inappropriate, the study plan is violated, or for administrative and/or other safety reasons.

Subjects must be withdrawn from the study treatment for the following reasons:

- In the investigator's medical judgment, further participation would be injurious to the subject's health or well-being.
- Consent is withdrawn by the subject or legal representative (such as parent or legal guardian).

- The study is terminated by the sponsor.
- The study is terminated by the local health authority or IRB/IEC.
- The subject has experienced an unacceptable toxicity or a toxicity that does not recover in 2 weeks.
Investigators who wish to continue treatment after a treatment delay of 2 weeks should consult with the sponsor's medical monitor for approval.
- Noncompliance with study treatment or procedure requirements.
- The subject is lost to follow-up.

6.6. Study Completion

6.6.1. Study completion criteria

Subjects will be considered completing the study if they met any of the following criteria:

- Subject dies and a date of death is available.
- Subject is known to have died; however, the date of death cannot be obtained.
(NOTE: every effort must be made to obtain the date of death.)
- Consent is withdrawn for any further contact related to this study.
- Subjects may choose to withdraw from the study at any time without penalty of jeopardizing their health care or loss of benefits to which the subject is otherwise entitled. Every reasonable effort should be made to determine the reason a subject withdraws prematurely, and this information should be recorded in the eCRF.
- The study is terminated by the sponsor.
- The study is terminated by the local health authority or IRB or IEC.

6.6.2. Withdrawal procedures

In the event that any subject discontinues study drug and, subsequently, withdraws from the study before completion, regardless of reason, reasonable efforts should be made to have the subject return for the EOT procedures to be completed. The date the subject was withdrawn from the study and the specific reason for withdrawal will be recorded in the eCRF.

If a subject is withdrawn from the study:

- The study monitor or sponsor must be notified.
- The reason(s) for withdrawal must be documented in the subject's medical record and in the eCRF.
- The EOT or early termination visit should be performed.

- Subjects must be followed for safety until the time of the follow-up visit or until study drug-related toxicities resolve, return to baseline, or are deemed irreversible, whichever is longer.

6.7. Concomitant Medications

No other approved or investigational anticancer treatment will be permitted during the study period. No other investigational drug may be used during treatment on this protocol, and concurrent participation in another clinical trial is not allowed.

Abemaciclib is predominantly cleared by oxidative metabolism via CYP3A4. Clinical drug interaction studies with a CYP3A inhibitor and CYP3A inducer significantly altered the PK of abemaciclib and its circulating major metabolites.

CYP3A inducers

Avoid concomitant use of CYP3A inducers and consider alternative agents.

CYP3A inhibitors

Avoid concomitant use of strong CYP3A inhibitors (for example, voriconazole) and use caution with coadministered moderate (for example, ciprofloxacin) or weak (for example, ranitidine) CYP3A inhibitors. If concomitant use cannot be avoided, abemaciclib dose adjustments may be required:

- Patients who must take CYP3A inhibitors such as clarithromycin, diltiazem, or verapamil should reduce the abemaciclib dose to 100 mg twice daily.
- Patients who must take itraconazole should reduce the abemaciclib dose to 50 mg twice daily.
- Patients who must take ketoconazole should reduce the abemaciclib dose to 50 mg once daily.
- Patients should avoid grapefruit or grapefruit juice.

Strong CYP3A inhibitors and/or inducers should not be used until the completion of the dose-limiting evaluation period.

Patients who receive nonsteroidal anti-inflammatory drugs (NSAIDs) on study should also receive peptic ulcer disease (PUD) prophylaxis with a histamine-2 (H2) blocker or proton pump inhibitor.

Narcotic analgesics, NSAIDs, ketorolac and triptans (e.g., sumatriptan) may be offered as needed for relief of pain or headaches. Antihistamines and decongestants may be offered for the treatment of sinus congestion.

Antibiotic prophylaxis should be used for invasive dental procedures.

Packed red blood cells, colony stimulating factors, and platelet transfusions should be administered as clinically indicated.

6.8. Treatment Compliance

All infusions (ADT) and oral intake of Abemaciclib will occur at the investigational site under the direct supervision of the Investigator or his or her designee.

6.9. Patient Enrollment

Patients will be manually enrolled by site research coordinator in Oncore database and assigned an 8-digit patient number. This 8-digit number will be used to identify patients throughout their participation in the trial. A regulatory binder will be provided and will include detailed instructions for the manual enrollment process.

6.10. Beginning and End of the Study

The study begins when the first subject signs the informed consent. The end of the study may be designated as the timepoint when all subjects have discontinued the study. At this point a database lock of the study may occur to allow the analysis of the study data.

7. ASSESSMENT OF EFFICACY

7.1. PSA serial measurements

Serum samples for assessment of PSA levels will be collected at all study visits and analyzed by the central laboratory. Additional assessments of PSA levels during the subject's participation in the study, either done for-cause or per standard of care, should be done through the central laboratory as well. Before the start of the study, sampling and storing procedures will be provided in a laboratory manual.

8. ASSESSMENT OF SAFETY

8.1. Safety Parameters

Safety will be characterized in terms of the incidence, timing, severity graded by the National Cancer Institute (NCI) Common Terminology Criteria for Adverse Events (CTCAE), Version 4.03, seriousness, and drug-relatedness of adverse events (AEs) and laboratory abnormalities. In addition, physical examination, vital signs, and ECOG performance status will be serially monitored. Laboratory safety analyses will be based on the data from which labs are collected, and will include hematology (including iron studies at baseline), serum chemistry (including liver and kidney function, and TSH), urinalysis, and coagulation profile (baseline only). Serum will also be assessed for immunogenicity to Abemaciclib (including anti-product antibody titers). In addition, single tracing 12-lead ECGs will be performed at the time points indicated in the Schedule of Assessments (Table 2). QT, PR and QRS intervals and heart rate will be captured. ECGs will also be collected as clinically indicated throughout the study.

